8.2.3 Interferon Signaling Ancillary Study

Principal Investigator: [name] Indiana University, Bloomington

Background and Rationale:

Interferons are known to induce a large number of genes, including transcription factors (STATs), kinases, anti-viral activities, and nucleases. It has been estimated from DNA microarrays that there may be as many as 300 genes whose expression is modified following interferon treatment. Many of these changes occur within 4-6 hours of treatment in vitro. Likewise changes in serum cytokines have been shown to occur in humans following interferon treatment. These cytokines in turn may induce other factors. Utilizing the approach of DNA microarrays, where we can examine a large number of changes in gene expression at the one time, we will look at patterns of changes in expression following treatment of patients with the combination of PEG-interferon and ribavirin. This will be done using RNA extracted from PBMC at early time points after the initiation of treatment. We are seeking to determine if there are major changes in responders, which are not seen in non-responders, and whether such changes can be linked to outcome of treatment. Additionally, we will examine whether there are any genetic differences in patterns between African Americans and Caucasian patients, and whether there are anti-viral mechanisms (e.g. PKR) that are non-functioning in some patients. The DNA array is only a first stage in this type of analysis, since any data received from the array has to be further analyzed by Northern analysis and quantitative PCR. We shall also examine the induction of cytokine genes as targets in DNA arrays. If we find increases in cytokine production, we will follow-up by measuring the levels of that cytokine in the serum. This should give a very comprehensive picture of the molecular changes that occur following interferon administration.

Study Aim:

To determine if unique cytokines induced by interferon-based therapy (early and late responses) are expressed differently in African Americans and Caucasians and responders and non-responders.

Study Endpoints:

- (a) Differences in cytokine gene expression (using DNA arrays) in flat, early and late responders, African Americans versus Caucasians
- (b) Differences in specific cytokine levels identified in (a) in serum for African Americans versus Caucasians and among the 3 response patterns
- (c) Differences in measured cytokine levels in cultured PBMCs from African Americans and Caucasians before and after interferon treatment (in vitro)
- (d) Differences in the early (12-24 hours following the start of antiviral therapy) expression of interferoninducible genes (PKR, oligo A synthetas, Mx protein, indole amine 2,3 dioxygenase or others identified by DNA array analyses) in African Americans and Caucasians

Study Population:

Minimum of n=72 with 6 groups of no less than 12 each (Groups: flat, rapid and slow response types for both African Americans and Caucasian groups).

Note: Since the response pattern will only be determined by week 4 of the study (based upon viral kinetic data), blood be obtained from all 400 patients up to and including week 4. However, only the 72 (or more) patients randomly selected for study (within groups defined by response pattern and race) will require blood draws beyond week 4.

Method for Analysis/Power Calculations:

Note: The power calculations for this study were done assuming either 2 or 3 responder groups (i.e., for some analyses the slow and fast responder groups will be combined) and with cytokine response treated as either a continuous or categorical variable. The power calculations are based on n=72, or the smallest sample size that will be used for this study.

Method 1: A chi-square test will be used to compare the proportions of treatment non-responders, treatment slow responders and treatment fast responders (i.e., 3 responder groups) that show a defined level (established *a priori*) of cytokine response. A sample size of 72 will yield an effect size of 0.37 (small to medium effect size). An example of proportions that could be found in the non-responders, slow-responders and fast responders, respectively, at an effect size of 0.37 is 10%, 30%, and 50%.

Method 2: A test for proportions will be employed to compare the proportion of treatment responders (slow and fast responders combined) who show a defined level of cytokine response compared to that of non-responders. Thus, these analyses are based on 2 responder groups. Given a sample size of 72 subjects and using a two-tailed test with α = 0.05, we will have 80% power to detect that 42% of responders have the cytokine response if 10% of the non-responders have the cytokine response.

Method 3: Using a one-way analysis of variance (ANOVA) test to compare the distributions of the level of cytokine response to treatment among slow responders, fast responders and non-responders (i.e., 3 responder groups). Given a sample size of 72 subjects and using an alpha of 0.05, two-tailed test, we will have 80% power to detect an effect size of 0.38, corresponding to a large effect size for ANOVA.²⁹

Method 4: A t-test to compare the distributions of the level of cytokine responses between treatment responders (slow and fast responders combined) versus non-responders. Thus, these analyses are based on 2 responder groups. Given a sample of 72 subjects and using a two-tailed test with $\alpha = 0.05$, we will have 80% power to detect a difference in the mean level of cytokine response between treatment responders and non-responders equal to an effect size of 0.68 (approximately two-thirds of a standard deviation). According to Cohen, an effect size for a t-test of 0.7 would be in the medium-large range.

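### Interferon-signaling ancillary study: race is in every endpoint and in the sampling, but none of the four stated methods or power figures includes race

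*Protocol*

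**What the plan says.** All of this is in Protocol section 8.2.3.

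- **Aim.** It asks whether cytokines induced by therapy "are expressed differently in African Americans and Caucasians and responders and non-responders".
- **Endpoints.** (a) is "Differences in cytokine gene expression (using DNA arrays) in flat, early and late responders, African Americans versus Caucasians". (b) concerns cytokine levels "in serum for African Americans versus Caucasians and among the 3 response patterns". (c) is "Differences in measured cytokine levels in cultured PBMCs from African Americans and Caucasians before and after interferon treatment (in vitro"). (d), on early expression of interferon-inducible genes, ends "or others identified by DNA array analyses) in African Americans and Caucasians". So (a) and (b) involve both race and response pattern, while (c) and (d) compare the races only.
- **Sample.** "Minimum of n=72 with 6 groups of no less than 12 each", the groups being three response patterns in each of two races, with random selection inside those groups.
- **Analysis and power.** The opening note says that power was worked out for two or three responder groups. Method 1: "A chi-square test will be used to compare the proportions of treatment non-responders, treatment slow responders and treatment fast responders". Method 2 compares two proportions, responders against non-responders. Method 3 is a one-way analysis of variance "to compare the distributions of the level of cytokine response to treatment among slow responders, fast responders and non-responders". Method 4 is a t-test of responders against non-responders. Race is not a factor, stratum or covariate in any of them, and no detectable race difference is given.

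**The concern.** The analysis block does not match the endpoints above it. Endpoints (c) and (d) have no stated test, and neither does the racial half of (a) and (b). Race is the subject of the whole trial, and the rationale of this section expects that as many as 300 genes may change expression. If the race analysis is chosen after the data are seen, with no declared detectable difference, a null result could be read as showing no racial difference when the sample could find only a large one.

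A second, smaller issue follows from the design. Race is a sampling stratum, and Methods 1-4 pool over it. If expression does differ by race, that variation enters the residual in Methods 3 and 4, which then fall short of their stated power. Methods 1 and 2 have no separate error term, but pooling over balanced strata should act in the same conservative direction; no loss was computed for them.

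**Working it through.** **1. Endpoints against methods**

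| Endpoint | Race | Response pattern | Stated method for pattern | Stated method for race |
|---|---|---|---|---|
| (a) | yes | yes | Methods 1-4 | none |
| (b) | yes | yes | Methods 1-4 | none |
| (c) | yes | no | not needed | none |
| (d) | yes | no | not needed | none |

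Other ancillary studies in the same protocol do handle race. Viral Genetics (8.2.1), with the same six-cell layout, states a Caucasian against African American test with its power. Patient Genetics (8.2.2) analyses within race and then stratifies or adjusts. The CD8 comparison (8.2.4) is made within racial groups.

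**2. The plan's own figures.** Inputs from 8.2.3: n = 72, two-sided alpha 0.05, three equal patterns of 24.

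- Method 1: noncentral chi-square, 2 df, noncentrality 72 × 0.37² = 9.86. Power is 80.9%.
- Method 3: noncentral F with 2 and 69 df, noncentrality 72 × 0.38² = 10.40. Power is 81.3%.

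Both reproduce the intended 80%.

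**3. Cost of leaving race out of Method 3.** Let D be the race difference in within-cell SD units. **D is an assumption; the protocol gives no value.** With equal numbers of each race in every pattern, the residual variance of the one-way model is about 1 + D²/4, so the effective effect size is 0.38 / √(1 + D²/4).

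| D (SD) | √(1 + D²/4) | effective f | power, race omitted | power, race in model |
|---|---|---|---|---|
| 0 | 1.000 | 0.380 | 81% | 81% |
| 0.25 | 1.008 | 0.377 | 81% | 81% |
| 0.5 | 1.031 | 0.369 | 79% | 81% |
| 1.0 | 1.118 | 0.340 | 72% | 81% |
| 1.5 | 1.250 | 0.304 | 61% | 81% |

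Direct simulation of six cells of 12, with pattern means -0.465, 0 and +0.465 SD (f = 0.465 × √(2/3) = 0.38), agrees: 81%, 79%, 72% and 59% at D = 0, 0.5, 1.0 and 1.5. The last row is therefore best read as about 60%.

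**4. Validity.** Simulated with no pattern effect, the one-way test rejects about 5% of the time at D = 0, 3.3% at D = 0.75 and 1.0% at D = 1.5. The two-way model stays near 5%. Omitting race is therefore conservative.

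**5. What 72 patients can say about race** (80% power, two-sided alpha 0.05)

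- Race overall, 36 v 36: 0.67 SD by noncentral t. Normal check: (1.96 + 0.8416) × √(2/36) = 0.66. As proportions, about 10% v 38%.
- Race within one response pattern, 12 v 12: 1.20 SD.
- Race-by-pattern interaction, 2 and 66 df: f = 0.37.

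**The case against.** **The block may be a set of sample-size scenarios, with the full list of tests left to an analysis plan.** Some weight. But the section is headed as analysis method as well as power, it names four tests, and they cover one of the two factors in its own endpoints.

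**Section 6.0 already supplies two-race tests.** It names the t-test or rank-sum test for continuous data and chi-square or exact tests for categorical data, but in the paragraph describing baseline data. Its other race analyses concern sustained response, HCV RNA and kinetic parameters. None is tied to gene expression or cytokines.

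**Method 4's effect size of 0.68 is already the race figure.** Numerically it is close, because 0.68 fits a 36 v 36 split (81% power). The protocol attaches it to responders against non-responders, however, and a reader would not know that it also serves for race.

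**The loss of power is hypothetical.** This stands. The aim is to find out whether expression differs, and no size is given. Up to 0.5 SD the loss is 2 to 3 points; about 10 points needs a difference near 1 SD.

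Three stronger readings are tempting, and the documents do not support them:

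- *That the response-group comparisons are biased or invalid.* The cells are balanced by race, so they are not.
- *That a race contrast could rest on 200 v 200, because early blood is drawn on all 400.* The section explains that collection by the fact that response pattern is unknown until week 4. It bases power on 72 and does not promise assays on everyone.
- *That cell results must be weighted back to each race's natural mix of patterns.* The section does not claim to estimate that quantity.

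**Conclusion.** The point holds in a limited form. Section 8.2.3 puts race in its aim, in all four endpoints and in its sampling, yet states no method and no power for race. That mismatch is the main finding, and it can be read directly from the text.

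The effect on the response-group tests is secondary. They stay valid and conservative. Method 3's power falls from about 81% to 79%, 72% or 60% for assumed race differences of 0.5, 1.0 or 1.5 SD, and is essentially unchanged for small ones. These figures assume six cells of exactly 12, equal variances and the same race shift in every response pattern.

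A reader should not infer that the design cannot address race. The six cells allow a race contrast of about 0.67 SD, and what is missing is the statement of it. The issue is confined to one ancillary study. The trial's primary endpoint and sample size are not affected.

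**What to change.** In section 8.2.3:

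1. Replace Methods 3 and 4 for continuous outcomes by a two-way analysis of variance with race and response pattern, testing the interaction. Responders against non-responders becomes a contrast within that model.
2. Replace Methods 1 and 2 for binary outcomes by Mantel-Haenszel tests or logistic regression stratified by race.
3. For endpoint (c), compute each patient's before/after change and compare it between races. The two-way analysis of single values does not deal with that pairing.
4. State the detectable race difference at n = 72: about 0.67 SD overall (36 v 36) and about 1.2 SD within one response pattern (12 v 12).

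The cost is wording plus one degree of freedom for race, or three with the interaction. Power for the response effect of 0.38 stays at 81%. No extra patients, blood or visits are needed.

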CD8+ studies (N = 100): 100 subjects with genotype 1a 20 will be consented later depending on their response to therapy. These power calculations are based upon unadjusted analyses, and fibrosis and viral load will be controlled for as potential confounding variables using logistic regression modeling.

Method for Analysis/Power Calculations:

CD4 Analyses

Method 1: A two-sample t-test will be utilized to compare the distributions of the number of cells that react between the responders and non-responders. The table below shows the power to detect various effect sizes with α = 0.05, using a two-sided test, and assuming that 33% of the Caucasians will respond to therapy and either 25% or 15% of the African Americans will respond to therapy. Note that effect sizes of 0.4, 0.5, and 0.6 would be considered to be small to medium.²⁹

Table 11							
Racial Group	Power	Proportion Responding To Therapy	Effect Size				
Caucasians	0.76	0.33	0.4				
African Americans	0.86	0.25	0.5				
African Americans	0.86	0.15	0.6				

Method 2: Logistic regression models with responder/non-responder as the outcome variable will be fit to test the detectable increase in the odds of responding for every standard deviation increase from the mean number of cells which show some reaction. These models will be based on both unadjusted and adjusted analyses.

The table below shows the detectable odds ratios from logistic regression analyses, based on 80% power and assuming that 33% of the Caucasians will respond, either 25% or 15% of the African Americans will respond, and a multiple correlation coefficient of 0.4 (i.e., the correlation between the independent variable of interest, the number of cells that react, with all the other independent variables). ³²

Table 12								
Racial Group	Proportion Responding	Odds Ratio (unadjusted)	Odds Ratio (adjusted)					
Caucasians	0.33	1.6	1.7					
African Americans	0.25	1.7	1.8					
African Americans	0.15	1.85	2.0					

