Example of Method 2: Given a sample size of 200 Caucasians patients and assuming that one-third will be responders, we will have 80% power to detect an odds ratio of 1.6 for every one standard deviation increase from the mean number of cells that react, using a two-tailed test and $\alpha = 0.05$. This can be interpreted as saying that the odds of being a responder increases by 60% for every one standard deviation increase in the number of cells that react. Adjusting for potential confounders, and assuming a multiple correlation coefficient of 0.4 between the number of cells that react and the other independent variables, we will have 80% power to detect an odds ratio of 1.7.

CD8 Analyses

The number of CD8 cells showing response will be categorized using a clinically meaningful cutpoint. Then the proportion of responders showing greater than the cut-off value of cell responses will be compared to that of the non-responders. This comparison will be done within the racial groups.

Assuming α = 0.05, two-sided test, there will be 80% power to detect a difference if 60% of the responders show greater than the cut-off value of cell responses and 20%, or fewer of the non-responders do. This corresponds to an odds ratio of approximately 6.4. In multivariable analyses, there will be 80% power to detect a difference in proportions between 60% in the responders and 15% or less in the non-responders, using a two-tailed test with alpha equal to 0.05, and assuming a multiple correlation coefficient between the covariate of interest (e.g., responder) and the other independent variables. This corresponds to an odds ratio of about 8.5. These effects are large, however, it is expected that the differences will be substantial and that these are reasonable estimates.

12/08/03

Table 13

Study	Number of Patients	Patient Specifications	Specimen	Minimum Volume per Timepoint
Viral Genetics ([name])	400	Initially, the Viral Genetics study will include at least 96 patients based upon early response pattern and race	Plasma	2 ml (5 ml whole blood)
Viral Kinetics	400		Plasma	2 ml (5 ml whole blood)
Pharmacokinetics	400		Serum	3 ml (7 ml whole blood)
Patient Genetics ([name])	400	NA	Whole blood	15 ml
Interferon Signaling ([name])	All up to and including 4 wks, at least 72 at post- treatment	For 72 (or more), equal number with each early response pattern and race	Whole blood	16 ml

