Immunology ([name])	400	All patients will have CD4+ T cell analysis	Whole blood	56 ml at pre for all; 32 ml at 8, 24 wks for all; 48 wks for responders; 56 ml (24 wks post treatment for 300 patients (not assigned to CD8 studies below)
	100 of 400 above	CD8 studies: Genotype 1a; 25 responders, 25 nonresponders in each of the Caucasian and African American racial groups	Whole blood	same schedule as above, but will have 136 ml (instead of 56 ml) drawn at 24 wks post treatment)
Liver Tissue (future studies)	Varies	NA	Liver	Residual from pathology requirements

Ancillary Studies and Viral Kinetics: Number of Patients, Specimen Type

12/08/03

Table 14

Ancillary Studies and Viral Kinetics: Specimen Timepoints and Total Volumes														
	Pre- Treatment		Treatment							Post-Treatment				
	Screen 2	BL Time 0	Day 1	Day 2	Wk 1 (Day 7)	Wk 2 (Day 14)	Wk 4 (Day 28)	Wk 8	Wk 12	Wk 24	Wk 48 Respond -ers only	Wk 24	Additional Follow-Up (4,12,36, 48 Wk) Responders Only	Any Follow-Up Visit***
Viral Genetics ([name])		5ml	5ml	5ml	5ml	5ml	5ml	5ml	5ml	5ml	5ml	5ml	5ml at each time	
Viral Kinetics		5ml	5ml	5ml	5ml	5ml	5ml	5ml	5ml	5ml	5ml	5ml	5ml	
Pharmacokinetics		7ml	7ml	7ml	7ml	7ml	7ml	7ml	7ml	7ml	7ml		7ml §	
Patient Genetics ([name])		15ml												
IFN Signaling ([name])		16ml	16ml	16ml	16ml	16ml	16ml							16ml (at least n=72)
Immunology CD4+ ([name])	56ml							32ml		32ml	32ml	56ml		
Immunology CD8+ ([name])	56ml*							32ml*		32ml*	32ml*	136ml**		
TOTAL Volume	56ml	48ml	33ml	33ml	33ml	33ml	33ml	49ml	17ml	49ml	49ml	66ml (n=300) 146ml (n=100)	10ml at each time + 7ml at follow-up wk 12	16ml (at least n=72)
TOTAL Liver (mm)	Varies											Varies		

Ancillary Studies and Viral Kinetics:	Specimen Timepoints and Total Volumes
---------------------------------------	---------------------------------------

 AL Liver (mm)
 Varies
 Varies

 *
 Will use blood from that taken for the CD4 study (i.e., additional blood will NOT be taken for CD8 at these time points).

 56 ml (= 7 CPT tubes); 32 ml (= 4 CPT tubes)

 **
 136 ml (= 17 CPT tubes) at post treatment week 24

*** Any post treatment visit is suitable, preferably week 24§ Follow-up week 12 for peginterferon alfa-2a only

APPENDIX 1

Proposed Action Criteria for Hepatic Adverse Events (ALT Flares)

1) ALT

Baseline Serum [ALT]	On-Treatment Serum [ALT]	Action
≤100	<200	None

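### Interferon-signaling Method 4 states 80% power at an effect size of 0.68, but the section's own groups give 24 against 48 and about 76.5% power; separately, one CD8 odds ratio should be 6.0, not 6.4

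*Protocol*

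**What the plan says.** **Interferon signaling, Method 4 (Protocol 8.2.3).** The t-test compares cytokine response "between treatment responders (slow and fast responders combined) versus non-responders". The power statement reads "Given a sample of 72 subjects and using a two-tailed test with $\alpha = 0.05$, we will have 80% power to detect" a mean difference "between treatment responders and non-responders equal to an effect size of 0.68 (approximately two-thirds of a standard deviation").

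**Group sizes (Protocol 8.2.3, Study Population).** The sample is set at "Minimum of n=72 with 6 groups of no less than 12 each", the cells being "Groups: flat, rapid and slow response types for both African Americans and Caucasian groups". The note before the four methods says that power is calculated at 72, the lowest number that will be studied. Table 13 asks for equal numbers in each combination of early response pattern and race.

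**CD8 analysis (Protocol 8.2.4 and Table 13).** Table 13 plans "25 responders, 25 nonresponders in each of the Caucasian and African American racial groups", and responders are compared with non-responders within race. The text states 80% power for 60% of responders against 20% or fewer of non-responders above the cut-off, and adds: "This corresponds to an odds ratio of approximately 6.4". The adjusted version is 60% against 15%, with an odds ratio of about 8.5.

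**The concern.** Two of the three response patterns are pooled in Method 4, so equal cells cannot give equal arms: the ratio is 1:2. For a fixed total, unequal arms reduce power. A detectable effect worked out for two arms of 36 would therefore overstate what 24 against 48 can show. The stated 0.68 is close to what 36 against 36 would give.

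The CD8 odds ratio is a direct function of the two percentages printed beside it, and it does not match them.

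What is at stake is the accuracy of stated design properties in two ancillary studies. The comparison of sustained virological response between the racial groups does not depend on either figure.

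**Working it through.** **Inputs for Method 4.** All come from section 8.2.3 and Table 13: N = 72, two-sided alpha 0.05, effect size d = 0.68, six equal cells. The flat pattern is taken as the non-responder group, since the methods name three groups (non-responders, slow, fast) against the three patterns (flat, slow, rapid).

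- Cell size: 72 / 6 = 12.
- Non-responders: 2 races × 12 = 24.
- Slow and fast pooled: 2 patterns × 2 races × 12 = 48.

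**Formula.** Two-sample t-test with 70 degrees of freedom and noncentrality d × √(n1·n2/(n1+n2)). The normal approximation is Φ(noncentrality − 1.96).

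**Looking for the source of the stated figure (36 against 36).**
- √(36 × 36/72) = √18 = 4.243, so the noncentrality is 0.68 × 4.243 = 2.885.
- Power is 81.2% by noncentral t, or Φ(0.925) = 82.3% by normal approximation.
- The effect detectable with 80% power is 0.67 by t, or 0.66 by normal approximation.

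An equal split therefore gives a result close to the stated 80% at 0.68.

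**At the design's own split (24 against 48).**
- √(24 × 48/72) = √16 = 4, so the noncentrality is 0.68 × 4 = 2.72.
- Power is 76.5% by noncentral t, or Φ(0.76) = 77.6% by normal approximation.
- The effect detectable with 80% power is 0.71 by t, or 0.70 by normal approximation.
- Holding both 0.68 and 80% at 1:2 takes between 26 against 52 (79.8%) and 27 against 54 (81.3%), that is 78 to 81 patients.

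**The other methods in the section.**

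| Method | Stated | Recomputed power |
|---|---|---|
| 1, chi-square, three groups | effect size 0.37 | 80.9% |
| 2, two proportions, 24 against 48 | 42% v 10%, 80% power | 83.8% pooled, 82.1% Fisher, 74.4% continuity-corrected |
| 3, ANOVA, three groups | effect size 0.38, 80% power | 81.3% |

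Methods 1 and 3 reproduce. Method 2 reaches its stated power at the design split by the pooled and Fisher tests. Method 4 falls short of 80% by either calculation.

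**CD8 odds ratios (section 8.2.4).**
- 60% against 20%: (0.6/0.4) / (0.2/0.8) = 1.5 / 0.25 = 6.0. Stated: about 6.4.
- 60% against 15%: (0.6/0.4) / (0.15/0.85) = 8.5. Stated: about 8.5, correct.
- For comparison, 60% against 19%: 1.5 / (0.19/0.81) = 6.39.

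**CD8 power at 25 against 25.**
- 60% against 20%: 84.5% pooled, 84.8% arcsine, 78.8% Fisher exact, 75.8% continuity-corrected. The pooled and arcsine tests meet the stated 80%, and Fisher is close to it.
- 60% against 15%, adjusted: the section gives no value for the multiple correlation coefficient. Assuming 0.4, as in the CD4 calculations, the effective size is 25 × (1 − 0.16) = 21 per group. Power is then 88.3% pooled or 79.6% continuity-corrected, so the stated 80% holds.

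**The case against.** **The gap is small.** The shortfall is 3.5 points by noncentral t or 2.4 by normal approximation, and the detectable effect moves only from 0.68 to 0.71. The protocol treats 72 as a minimum, and it already draws blood from all 400 participants through week 4. One more patient per cell would bring power at 0.68 to 79.8%. All of this stands and makes the point minor. It does not make the figure right, because the section says that its power figures are for 72.

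**The odds ratio may be rounding.** A solved proportion of about 19%, printed as 20%, would explain 6.4, and the text hedges both the percentage and the odds ratio. That is a plausible origin, but the two printed numbers still disagree, while the neighbouring 8.5 agrees with its percentages.

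**A reader might infer that the CD8 power statements fail as well.** The recomputation does not support this. Both 80% statements are reproduced or met under standard tests.

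**A reader might also infer that 25 African American genotype 1a responders cannot be found.** The reasoning would take the lower rate in "either 25% or 15% of the African Americans will respond to therapy" and the genotype shares in section 1.1 (genotype 1 in 91%, 1b in 36%): 200 × 15% × (91 − 36)/91 ≈ 18. The documents do not establish this, for four reasons:
- The 15% is the pessimistic alternative in the CD4 tables, and the CD8 paragraph does not use it.
- At 25%, the rate that section 6.0 uses for its multivariable calculation, the same arithmetic gives 200 × 25% × 0.60 = 30, more than 25.
- The genotype shares come from population surveys, not from trial enrolment.
- The CD8 text does not say whether a responder is someone with sustained response or someone HCV RNA negative at treatment week 24, the meaning in section 3.1.

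**Conclusion.** Method 4 is wrong as written. With 72 subjects in six equal cells, the test compares 24 with 48, and power at 0.68 is about 76.5% (77.6% by normal approximation), not 80%. The effect detectable with 80% power is 0.71. This rests on the flat pattern being the non-responder group and on the sample being exactly 72, both of which follow from the section's own text.

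The CD8 odds ratio for 60% against 20% is 6.0, not 6.4. This is plain arithmetic and drives no sample size or test.

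Both are minor corrections in ancillary studies. Nothing here shows that the CD8 comparison lacks its stated power, that its groups cannot be filled, or that the remaining interferon-signaling methods rest on a wrong split.

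**What to change.** In section 8.2.3, Method 4, either give the detectable effect as 0.71 with 80% power, or keep 0.68 and state power of about 76%. In both cases name the 24 against 48 split. In section 8.2.4, CD8 Analyses, change the odds ratio for 60% against 20% from 6.4 to 6.0. Leave the CD8 power statements, the 8.5 and the group sizes as they are.

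The cost is two text edits and a slightly less favourable detectable effect. No patients, samples or analyses are added.
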